It has now been shown in phase 1-3 clinical trials that MDV3100 demonstrates a similar endocrine response profile (hypergonado-tropic hypergonadism) as other marketed AR antagonists. Given the strong in vitro data showing superiority to bicalutamide, the nonclinical data demonstrating few toxicities, robust clinical data from the phase 1-3 showing anti-tumor effect, the favorable overall safety profile of MDV3100 in the phase 1-3 completed and ongoing studies, together with the manageable safety profile, the benefits of studying MDV3100 outweigh the risks involved. Patients with locally advanced or metastatic prostate cancer may benefit from a compound that offers improved efficacy to traditional anti-androgens coupled with a less unfavorable side effect profile when compared to LHRH analogues. The proposed total daily dosage (160 mg) in the proposed study seems to be acceptable in light of the safety and efficacy data obtained to date. The identified risk of seizure and potential risks described for currently approved anti-androgens will be monitored through clinical follow-up and by routine laboratory assessments. The FDA's guidance for Drug-Induced Liver Injury (DILI) will also be followed. In summary, the benefit risk profile for patients participating in the study that will be treated with MDV3100 is considered to be favorable as potential benefits exceed identified and potential risks. Please refer to the most

current edition of the MDV3100 Investigator's Brochure for complete information on risk/benefit.

The 9785-CL-0121 is an extension study to prior MDV3100 studies and subjects will only participate in this extension study if they have been actively enrolled and have completed MDV3100 treatment in the prior MDV3100 study and when administration of MDV3100 is deemed by the investigator/treating physician to be in the patient's best interest. Routine subject disease management will assess the risks and benefits of the continued use of MDV3100. The possibility of offering patients who benefit from MDV3100 in the preceding study continuous medication within the boundaries of an extension study is in compliance with the ethical principles for oncology phase 1 studies.

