5.1.2 Increase or Reduction in Dose of the Study Drugs

Subjects who experience a grade 3 or greater toxicity that cannot be ameliorated by the use of adequate medical intervention should have their treatment interrupted until the toxicity improves to a grade 2 or lower severity. Subjects may subsequently be restarted on study drug at a reduced dose with the written approval of the sponsor. An increase in dose is not permitted.

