5.4.2.1 Adverse Events of Possible Hepatic Origin

Subjects with AEs of hepatic origin accompanied by Liver Function Test (LFT) abnormalities should be carefully monitored.

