5.5.5 Criteria for Defining the Severity of an Adverse Event

Severity of AEs will be graded according to the Common Terminology Criteria for Adverse Events (CTCAE) v. 4.0 of the National Cancer Institute (NCI) Cancer Therapy Evaluation Program (CTEP). For terms not specified within NCI-CTCAE, the following guideline should be used to determine grade as below in [Table 4](#)

Table 4 Criteria for Severity of Adverse Event Terms Not Specified Within NCI-CTCAE

Grade	Description
1	Mild; asymptomatic or mild symptoms, clinical or diagnostic observations only; intervention not indicated
2	Moderate; minimal, local or noninvasive intervention indicated; limiting age-appropriate instrumental activities of daily living
3	Severe or medically significant but not immediately life-threatening; hospitalization or prolongation or hospitalization indicated; disabling; limiting self care activities of daily living
4	Life-threatening consequences; urgent intervention indicated
5	Death related to AE

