12.2 Appendix 2: Liver Safety Monitoring and Assessment

If laboratory testing for a subject enrolled in study and receiving study drug reveals an increase of serum aminotransferases (AT) to $> 3X$ ULN, or bilirubin $> 2X$ ULN, at least all four of the usual serum hepatic measures (ALT, AST, ALP, and bilirubin [TBL]) should be repeated. Testing should be repeated within 48-72 hours of notification of the test results. For studies for which a central laboratory is used, alerts will be generated by the central lab regarding moderate and marked liver abnormality to inform the investigator, study monitor and study team. Subjects should be asked if they have any symptoms suggestive of hepatobiliary dysfunction.

Definition of Liver Abnormalities

Confirmed abnormalities will be characterized as moderate and marked where ULN:

Moderate	ALT or AST $> 3 \times \text{ULN}$	or	Total Bilirubin $> 2 \times \text{ULN}$
Marked	$> 3 \times \text{ULN}$	and	$> 2 \times \text{ULN}$

In addition, the subject should be considered to have marked hepatic abnormalities for any of the following:

- ALT or AST $> 8X$ ULN
- ALT or AST $> 5X$ ULN for more than 2 weeks
- ALT or AST $> 3X$ ULN and INR > 1.5
- ALT or AST $> 3X$ ULN with the appearance of fatigue, nausea, vomiting, right upper quadrant pain or tenderness, fever, rash and/or eosinophilia ($> 5\%$).

The investigator may determine that abnormal liver function results, other than as described above, may qualify as moderate or marked abnormalities and require additional monitoring and follow-up. Discontinuation of treatment must occur if subject has marked abnormalities. In addition, if closed monitoring for a subject with moderate hepatic laboratory tests is not possible, drug should be discontinued.

Follow-up Procedures

Confirmed moderate and marked abnormalities in hepatic functions should be thoroughly characterized by obtaining appropriate expert consultations, detailed pertinent history, physical examination and laboratory tests. The site should complete the Liver Abnormality Case Report Form (LA-CRF) or an appropriate document. Subjects with confirmed abnormal liver function testing should be followed as described below.

Confirmed moderately abnormal liver function tests (LFTs) should be repeated 2-3 times weekly then weekly or less if abnormalities stabilize or the study drug has been discontinued and the subject is asymptomatic.

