Marked hepatic liver function abnormalities, in the absence of another etiology, may be considered an important medical event and reported as a Serious Adverse Event (SAE). The

sponsor should be contacted and informed of all subjects for whom marked hepatic liver function abnormalities possibly attributable to study drug are observed.

To further assess abnormal hepatic laboratory findings, the investigator is expected to:

- Obtain a more detailed history of symptoms and prior or concurrent diseases. Symptoms and new onset-diseases should be recorded as 'adverse events' on the AE page of eCRF. Illnesses and conditions such as hypotensive events, and decompensated cardiac disease that may lead to secondary liver abnormalities should be noted. Non-alcoholic steatohepatitis (NASH) is seen in obese hyperlipoproteinemic, and/or diabetic patients and may be associated with fluctuating aminotransferase levels. The investigator should ensure that the medical history form captures any illness that pre-dates study enrollment that may be relevant in assessing hepatic function.
- Obtain a history of concomitant drug use (including non-prescription medication, complementary and alternative medications), alcohol use, recreational drug use, and special diets. Medications, including dose, should be entered on the concomitant medication page of eCRF. Information on alcohol, other substance use, and diet should be entered on the LA-CRF or an appropriate document.
- Obtain a history of exposure to environmental chemical agents
- Based on the subject's history, other testing may be appropriate including:
 - acute viral hepatitis (A,B, C, D, E or other infectious agents)
 - ultrasound or other imaging to assess biliary tract disease
 - other laboratory tests including INR, direct bilirubin.
- Consider gastroenterology or hepatology consultations.
- Submit results for any additional testing and possible etiology on the LA-CRF or an appropriate document.

Study Discontinuation

In the absence of an explanation for increased LFTs, such as viral hepatitis, pre-existing or acute liver disease or exposure to other agents associated with liver injury, the subject may be discontinued from the study. The investigator may determine that it is not in the subject's best interest to continue study enrollment.

Discontinuation of treatment must occur if:

- ALT or AST > 8X ULN
- ALT or AST > 5X ULN for more than 2 weeks
- ALT or AST > 3X ULN and (TBL > 2X ULN or INR > 1.5)

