Discontinuation of treatment should be considered if:

- ALT or AST > 3X ULN with the appearance of fatigue, nausea, vomiting, right upper quadrant pain or tenderness, fever, rash and/or eosinophilia (> 5%).

In addition, if close monitoring for a subject with moderate or marked hepatic laboratory tests is not possible, drug should be discontinued.

Reference

Guidance for Industry titled “Drug-Induced Liver Injury: Premarketing Clinical Evaluation” issued by FDA on July 2009.

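### Appendix 2 allows weekly or sparser liver tests for a stable ALT or AST above 5X ULN on drug, and ties no test to the mandatory two-week stop

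*Protocol*

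**What the plan says.** All the operative text is in Protocol Appendix 2 (Section 12.2).

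- **Classification.** ALT or AST above 3X ULN alone is moderate. It becomes marked if accompanied by bilirubin above 2X ULN, INR above 1.5 or listed symptoms, if it exceeds 8X ULN, or under the duration criterion: "ALT or AST > 5X ULN for more than 2 weeks".
- **Consequence.** "Discontinuation of treatment must occur if subject has marked abnormalities". The duration criterion appears again in the list of mandatory discontinuations.
- **Testing schedule.** A confirmed moderate abnormality "should be repeated 2-3 times weekly then weekly or less if abnormalities stabilize". Testing may also be reduced once the drug has been stopped. The sentence ends with a condition that the subject is asymptomatic; whether this governs both branches is unclear.
- **Dated retest.** The only one is the confirmation within 48 to 72 hours of notification, in Appendix 2 and Section 5.4.3.1.
- **Backstop.** "if close monitoring for a subject with moderate or marked hepatic laboratory tests is not possible, drug should be discontinued". Close monitoring is not given an interval.

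Elsewhere, Section 5.1.2 interrupts drug for a "grade 3 or greater toxicity that cannot be ameliorated by the use of adequate medical intervention". Section 5.4.2.1 says: "Subjects with AEs of hepatic origin accompanied by Liver Function Test (LFT) abnormalities should be carefully monitored". Section 1.4 says that the FDA's "guidance for Drug-Induced Liver Injury (DILI) will also be followed".

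**The concern.** A mandatory stop that depends on elapsed time needs a test able to show that the time has passed with the value still raised. Here the two rules pull in opposite directions. An isolated, asymptomatic ALT or AST above 5X and up to 8X ULN counts as moderate until it has lasted more than 2 weeks. If it holds steady it reaches the mandatory stop, yet holding steady is also the condition for testing less often. A site can follow the schedule exactly and still see the stop late, with the subject on drug in the meantime.

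Nothing central would prompt the site. Appendix 2 describes laboratory alerts only for studies using a central laboratory, and Sections 5.4.3 and 8.1.1 specify local laboratories. At stake is some days of continued dosing in a subject who should have stopped.

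**Working it through.** The plan states no figure here, so there is none to reproduce. The check has two parts.

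**1. Does any text fix a test at the deadline?**

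| Provision | Effect on test timing |
|---|---|
| 48 to 72 hour repeat (Section 5.4.3.1, Appendix 2) | Confirmation only; if it recurred after every raised result it would contradict the weekly step-down |
| Other repeat tests (Section 5.4.3) | Investigator's discretion |
| AE and laboratory follow-up (Sections 5.5.7, 6.1) | Follow-up required, no test date |
| Careful or close monitoring (Section 5.4.2.1, Appendix 2) | No interval |
| Grade 3 interruption (Section 5.1.2) | May pause drug; no test date |
| Scheduled visits (Table 1) | Every 12 weeks after day 85, then every 24 weeks from week 85 |
| SAP Section 7.5.2 | Lists raised liver values; sets no tests |

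None does. The asymptomatic condition does not remove the case, because symptoms from the list would already make the abnormality marked.

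**2. How late can the stop be seen?**

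Inputs: the duration criterion is more than 2 weeks (Appendix 2), so with day 0 as the first value above 5X ULN, day 15 is the first whole day that meets it. Weekly is the only reduced interval that the text names. The spacing within a week is my assumption: gaps of 3 and 4 days for twice weekly, and of 2, 2 and 3 days for three times weekly.

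Lag = day of the first test on or after day 15, minus 15. If day 15 can fall anywhere in the 7-day test cycle, a gap of g days contributes lags 0, 1, ..., g − 1. Hence:

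- maximum lag = (largest g) − 1
- mean lag = sum of g(g − 1)/2 over the gaps, divided by 7

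| Schedule | Lags over the seven phases | Maximum | Mean |
|---|---|---|---|
| Weekly (7) | 0,1,2,3,4,5,6 | 6 | 21/7 = 3.00 |
| Twice weekly (3, 4) | 0,0,1,1,2,2,3 | 3 | (3 + 6)/7 = 1.29 |
| Three times weekly (2, 2, 3) | 0,0,0,1,1,1,2 | 2 | (1 + 1 + 3)/7 = 0.71 |

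The worst weekly case is a series aligned to day 0. It tests on days 7, 14 and 21; day 14 is not yet more than 2 weeks, so day 21 is the first test that can show the criterion.

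Avoidable lag of weekly testing:

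- against twice weekly: worst case 6 − 3 = 3 days, mean 3.00 − 1.29 = 1.71
- against three times weekly: worst case 6 − 2 = 4 days, mean 3.00 − 0.71 = 2.29
- against a test on day 15 exactly: worst case 6 days, mean 3.00
- against a test by day 17 at the latest: worst case 6 − 2 = 4 days

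For testing less often than weekly the same formula gives a maximum of g − 1 days, but the documents supply no g.

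**The case against.** The best reply is that the appendix, read as a whole, already covers this. A mandatory stop based on duration obliges the investigator to find out whether the duration has been reached, and testing too sparse to tell is hardly close monitoring. The investigator may reclassify an abnormality as marked at any time, which brings the stop forward. Confirmed abnormalities require expert consultation and a full work-up, and an unexplained rise may itself lead to discontinuation. The step-down is written for all moderate cases, including 3X to 5X ULN and subjects already off drug, and needs a prior judgement that values are stable. The grade 3 rule may well have interrupted drug already.

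Much of this stands: these clauses reduce the number of cases. None sets a test date, though, and a general step-down that does not exclude values above 5X ULN leaves the site free to apply it there. How far the grade 3 rule helps cannot be checked. Section 5.5.5 says "Severity of AEs will be graded according to the Common Terminology Criteria for Adverse Events (CTCAE) v. 4.0", but the ALT and AST cut-offs are not reproduced, and the rule applies only to toxicity that medical intervention cannot ameliorate. The documents likewise reproduce no interval from the FDA guidance.

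Three further objections limit the importance of the point. Day 0 is the first detected value, and with scheduled tests 12 or 24 weeks apart the true onset may be much earlier. The half-life is about 1 week (Section 5.1.3.2), so stopping a few days sooner changes exposure only modestly. Amendment 4 is closing the study.

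A reader might infer that the stop is disabled, or that a plateau could go unseen until the next scheduled visit. The text does not support either. The stop binds whenever the criterion is met, and a lapse of all interim testing would breach both the follow-up schedule and the close-monitoring clause.

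**Conclusion.** The gap is real and small. Appendix 2 lets testing fall to weekly or less for a subject on drug with a stable ALT or AST above 5X ULN, and nothing requires a test when the mandatory stop falls due. At weekly testing the stop is seen 0 to 6 days after day 15 (mean 3.0); against twice weekly the excess is at most 3 days. A longer delay is possible only through the unlimited further reduction, and I put no size on it.

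The figures assume whole-day timing, immediate results, even spread over the seven phases and the within-week spacing stated above. Moving the start of the clock, for example to the confirmation test, shifts day 15 but leaves the lags unchanged. The number of subjects affected is not given and may be very small. No endpoint or planned analysis is affected, and it would be wrong to read this as a flaw in the safety analysis. It is a cheap improvement to subject protection.

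**What to change.** Add to the follow-up paragraph of Appendix 2:

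> The reduction to weekly or less does not remove the need for a timed test. For a subject still on study drug whose ALT or AST has been > 5X ULN and has not been shown to fall to 5X ULN or below, a liver panel (ALT, AST, ALP, TBL) is obtained on day 15 (window day 15 to 17) after the first such value, and study drug is stopped if ALT or AST is still > 5X ULN. If a value falls to 5X ULN or below and later rises above it, the count restarts at the new value.

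The window makes the test workable and caps the lag at 2 days, and the last sentence settles how a rebound is counted. Subjects who have recovered or are off drug are not burdened.

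The clinical cost is an occasional extra local liver panel; Section 5.8 already allows additional blood for monitoring an abnormality. Under Section 8.3.3 the change has to be documented as an amendment, so with the study closing it is best bundled with any other change.

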5.4.3.1 Abnormal Liver Function Tests

If laboratory testing for a subject enrolled in a study and receiving study drug reveals an increase of serum aminotransferases (AT) to > 3x ULN, or bilirubin > 2x ULN, at least all four of the usual serum measures (ALT, AST, ALP, and total bilirubin [TBL]) should be repeated within 48 - 72 hours of notification of the test results. See [Appendix 2](#) (Liver Safety Monitoring and Assessment) for additional information on monitoring and assessment of abnormal liver function tests.

Laboratory assessments must be obtained prior to study drug administration.

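### Appendix 2 makes ALT/AST > 3x ULN with INR > 1.5 a mandatory stop, but nothing in the protocol calls for an INR when ALT/AST exceeds 3x ULN

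*Protocol*

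**What the plan says.** **The rule.** Protocol Appendix 2 brings INR into a mandatory stop by two routes. Under Study Discontinuation, the list of results that oblige treatment to stop includes "ALT or AST > 3X ULN and (TBL > 2X ULN or INR > 1.5". Under Definition of Liver Abnormalities, ALT/AST > 3x ULN with INR > 1.5 is one of the *marked* abnormalities, and "Discontinuation of treatment must occur if subject has marked abnormalities".

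**The tests asked for.** After ALT/AST > 3x ULN or bilirubin > 2x ULN, Section 5.4.3.1 says that "at least all four of the usual serum measures (ALT, AST, ALP, and total bilirubin [TBL]) should be repeated", within 48-72 hours. Appendix 2 says the same: "at least all four of the usual serum hepatic measures (ALT, AST, ALP, and bilirubin [TBL]) should be repeated". Neither place names INR.

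**The work-up.** Appendix 2 says that confirmed abnormalities "should be thoroughly characterized by obtaining appropriate expert consultations, detailed pertinent history, physical examination and laboratory tests", without naming the tests. Its itemised list then says that, depending on the subject's history, "other testing may be appropriate including" several items, one of which is "other laboratory tests including INR, direct bilirubin".

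**Elsewhere.** The routine panels (Sections 5.4.3.2 and 5.4.3.3, Appendix 1) contain no INR or other coagulation test. The only other INR instruction is extra monitoring for subjects who take warfarin (Synopsis, Concomitant Medication; Section 5.1.3.2). It is not linked to ALT or AST.

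**The concern.** A mandatory stop works only if each of its inputs is measured when the rule could apply. Here one input is optional. A subject with raised aminotransferases, bilirubin not above 2x ULN and an INR > 1.5 that nobody measured is classed as *moderate* and may continue treatment, although the protocol intends him to stop.

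The steps that follow from a *marked* classification are lost as well: the 24-hour contact with the sponsor (Section 5.4), and the prompt in Appendix 2 to consider reporting the finding as an SAE. The site would have committed no deviation.

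**Working it through.** No figure in the plan needs reproducing. The check is whether each laboratory input to the *marked* definition is matched by a test that the protocol asks for.

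**Step 1: inputs against tests.**

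| Input | Supplied by |
|---|---|
| ALT | all visits; 48-72 hour repeat |
| AST | all visits; 48-72 hour repeat |
| Total bilirubin (TBL) | all visits; 48-72 hour repeat |
| Eosinophils | WBC differential at all visits (assuming that it reports eosinophils) |
| INR | no scheduled or repeat test; discretionary in the work-up; monitored in warfarin users only |

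INR is 1 of 5 inputs and the only one without a test prompted by the schedule or by the liver result.

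**Step 2: when INR alone decides.** Suppose that INR is truly > 1.5 and the subject takes no anticoagulant. Cross the other criteria:

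- ALT/AST band: > 3-5x; > 5-8x for up to 2 weeks; > 5-8x for more than 2 weeks; > 8x ULN (4 bands)
- TBL: at or below 2x, or above 2x ULN (2 states)
- listed symptoms or eosinophilia: no or yes (2 states)

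This gives 4 x 2 x 2 = 16 combinations. Remove those where another criterion already forces the stop:

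- The two upper ALT/AST bands: 2 x 2 x 2 = 8, leaving 16 - 8 = 8.
- The two lower bands with TBL > 2x ULN: 2 x 2 = 4, leaving 8 - 4 = 4.

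The remaining 4 are the two lower bands with TBL at or below 2x ULN, with or without symptoms. Here Appendix 2 disagrees with itself. Its definition makes ALT/AST > 3x ULN with symptoms or eosinophilia *marked*, hence a mandatory stop. Its Study Discontinuation lists make the same finding only a reason to consider stopping.

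| Reading of Appendix 2 | Combinations where a missing INR removes the mandatory stop |
|---|---|
| Definition of *marked* (symptoms already decisive) | 4 - 2 = 2 of 16 |
| Study Discontinuation lists (symptoms not decisive) | 4 of 16 |
| Either reading, INR measured at the repeat | 0 of 16 |

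These are counts of logical combinations. They carry no information on how often each occurs.

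**Step 3: does any other provision require the INR?**

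- The four repeat tests are stated as a minimum. More are allowed, but none is asked for.
- The general work-up mentions laboratory tests without naming any, and the itemised list that follows makes INR discretionary.
- Liver tests for confirmed moderate abnormalities are repeated 2-3 times weekly at first, and drug is stopped if close monitoring is not possible. Neither provision brings in INR.
- The central-laboratory alerts in Appendix 2 do not apply, because this study uses local laboratories (Sections 5.4.3 and 8.1.1).
- Scheduled visits, 24 weeks apart from week 85, do not include INR.

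**The case against.** The best defence is that a competent investigator will order the INR anyway. The repeat set is a floor. Confirmed abnormalities are to be worked up thoroughly. INR is named in the *marked* definition, in the stop list and in the work-up list, so anyone who applies Appendix 2 sees that it matters. The investigator may also class other results as *marked*, and may discontinue a subject with unexplained rises. The Liver Abnormality CRF may ask for INR, but the form is not in the documents, so this cannot be checked. All of this lowers the chance of harm. None of it requires the test, so the rule can still go unassessed at a compliant site.

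A second objection stands and shapes the remedy. Warfarin is discouraged but allowed, with INR monitoring. An anticoagulated subject can have INR > 1.5 for reasons unrelated to the liver. Asking for INR at every ALT/AST > 3x ULN while leaving the criterion untouched would produce more mandatory stops of that kind, in subjects judged to benefit from treatment. The problem already exists in the criterion, but routine testing would bring it out more often.

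A third, smaller objection also stands: the repeat itself is worded as a *should*. An added INR should not be more binding than the four tests it accompanies.

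A reader might go further and infer that INR is never measured in this study, or that liver monitoring as a whole fails. The documents support neither. Warfarin users are monitored, investigators may order the test, and the other stop criteria rest on tests that are scheduled or repeated.

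**Conclusion.** The gap is real and narrow. It affects a subject with ALT/AST > 3x ULN (not > 8x, and not > 5x for more than 2 weeks), TBL at or below 2x ULN, and an unmeasured INR > 1.5. Under the *marked* definition it is confined to subjects without listed symptoms or eosinophilia. Under the Study Discontinuation lists it extends to those with them. In both cases the protocol intends a mandatory stop that its own testing instructions may never reveal.

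A reader might turn 2 of 16 or 4 of 16 into a miss rate of 12.5% or 25%. That is not supported, because the combinations are not equally likely and the documents give no frequencies. The group is probably small, and the benefit of a change is limited to subjects still on treatment in a study that the sponsor is closing. The threshold is not in dispute. No endpoint or analysis is affected.

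This is a cheap patient-safety improvement of low priority. The conclusion rests on the text of the two documents and on the assumption that no form or manual outside them requires the INR.

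**What to change.** Make two changes together.

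1. In Section 5.4.3.1 and in Appendix 2, after the sentence on the 48-72 hour repeat, add: *If ALT or AST is > 3x ULN, INR should also be measured at this repeat.*
2. In Appendix 2, attach to the INR > 1.5 criterion, in both the definition of marked abnormalities and the mandatory discontinuation list: *For subjects on warfarin or another anticoagulant that raises INR, an INR > 1.5 counts only if it is above the subject's therapeutic range or not explained by anticoagulation, as judged by the investigator with the sponsor's medical expert.*

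Keep INR in the discretionary list for other hepatic findings, such as bilirubin > 2x ULN alone, and for later re-testing. The change secures one INR at the repeat, and later ones stay at the investigator's discretion. It does not settle the disagreement within Appendix 2 about symptoms. No SAP change is needed.

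The cost is one added assay at an unscheduled draw that the protocol already specifies. Section 5.8 allows extra blood when abnormalities are found, and Appendix 2 already sends additional results to the liver CRF. Because the amendment affects subject safety, Section 8.3.3 requires IRB/IEC approval before it is implemented. With the study closing, that approval is the main argument for leaving the text alone.
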